## 3. Procedures During Administration of Investigational Medicinal Product (Open-Label Treatment Period [Visits 5 through 7, Days 84±3 through 140±3])

#### Visit 5, Day 84±3 days

The following procedures and assessments will be performed predose at visit 5:

- Perform clinical laboratory tests (serum chemistry, hematology and coagulation, and urinalysis).
- Perform a full physical examination (including weight).
- Perform 12-lead ECG in triplicate.

- Perform vital signs measurements (systolic and diastolic blood pressure, pulse, and body temperature).
- Perform a serum β-HCG test for women of childbearing potential.
- Review study compliance.
- Complete and review electronic headache diary.
- Obtain a 4 mL blood sample for plasma concentration of IMP.
- Obtain a 5 mL blood sample for serum ADA assay.
- Obtain an 18.5 mL blood sample and a urine sample for biomarkers analysis.
- Collect a 1 mL saliva sample for biomarker analysis.
- Inquire about adverse events.
- Complete HIT-6, SF-12, SCAT-3, PGIC, and C-SSRS Since Last Visit version questionnaires.

The following procedures and assessments will be performed at visit 5 following predose procedures and assessments:

- Administer IMP.
- Perform injection site assessments immediately (+10 minutes) and 1 hour (±15 minutes) after completing IMP administration. Additional injection site assessments may be performed based on the severity of any observed injection site reaction and/or injection site pain. See Section 7.9 of the protocol for additional details.
- Evaluate for anaphylaxis or hypersensitivity reactions.
- Inquire about concomitant medication.
- Inquire about postdose adverse events before the patient leaves the investigational center.
- Complete the Special Protocol Headache questionnaire. (to be completed at visit 5 and as the last study procedure at visit 8.)

#### Visit 6, Day 112±3 days

The following procedures and assessments will be performed predose at visit 6:

- Perform clinical laboratory tests (serum chemistry, hematology and coagulation, and urinalysis).
- Perform 12-lead ECG in triplicate.
- Perform vital signs measurements (systolic and diastolic blood pressure, pulse, and body temperature).
- Obtain a 4 mL blood sample for plasma concentration of IMP.
- Obtain an 18.5 mL blood sample for biomarker analysis.

- Collect a 1 mL saliva sample for biomarker analysis.
- Inquire about adverse events.
- Complete the HIT-6, SF-12, PGIC and C-SSRS Since Last Visit version questionnaires.

The following procedures and assessments will be performed at visit 6 following predose procedures and assessments:

- Administer IMP.
- Perform injection site assessments immediately (+10 minutes) and 1 hour (±15 minutes) after completing IMP administration. Additional injection site assessments may be performed based on the severity of any observed injection site reaction and/or injection site pain. See Section 7.9 of the protocol for additional details.
- Evaluate for anaphylaxis or hypersensitivity reactions.
- Inquire about concomitant medication.
- Inquire about postdose adverse events before the patient leaves the investigational center.

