# 3.5. Schedule of Study Procedures and Assessments

Study procedures and assessments with their time points are presented in Table 1. Detailed descriptions of each method of procedures and assessments are provided in Section 6 (efficacy assessments), Section 7 (safety assessments), and Section 8 (pharmacokinetics and other assessments). Study procedures and assessments by visit are listed in Appendix H.

**Table 1:** Study Procedures and Assessments

Study period	Pretreatment (including screening visit and baseline period)	Double-blind treatment period (visit/day or week)		Open-label period (visit/day or week)				
Visit number	V1 a	V2	V3	V4	V5	V6	V7	V8 b
Day and allowed time windows	Day -28 to -1 (+3 days)	Day 0±3 days	Day 28±3 days	Day 56± 3 days	Day 84±3 days	Day 112 ±3 days	Day 140±3 days	Day 168±3 days
Procedures and assessments	Screening	Randomization Week 0 Dose 1	Week 4 Dose 2	Week 8 Dose 3	Week 12 Dose 4	Week 16 Dose 5	Week 20 Dose 6	Week 24 EOT/EOS/ET
Informed consent	X							
Inclusion and exclusion criteria	X	X						
Assign randomization/treatment number		X						
Medical and psychiatric history	X							
Prior medication and treatment history c	X							
Record demographic characteristics	X							
Adverse events inquiry d,e,f	X	X	X	X	X	X	X	X
Concomitant medication inquiry f	X	X	X	X	X	X	X	X
Clinical laboratory tests (serum chemistry, hematology and coagulation, and urinalysis) g	X	X	X	X	X	X	X	Х
Full physical examination h	X	X			X			

Study period	Pretreatment (including screening visit and baseline period)	Double-blind treatment period (visit/day or week)		Open-label period (visit/day or week)				
Visit number	V1 a	V2	V3	V4	V5	V6	V7	V8 b
Day and allowed time windows	Day -28 to -1 (+3 days)	Day 0±3 days	Day 28±3 days	Day 56± 3 days	Day 84±3 days	Day 112 ±3 days	Day 140±3 days	Day 168±3 days
Procedures and assessments	Screening	Randomization Week 0 Dose 1	Week 4 Dose 2	Week 8 Dose 3	Week 12 Dose 4	Week 16 Dose 5	Week 20 Dose 6	Week 24 EOT/EOS/ET
Electrocardiography i	X	X	X	X	X	X	X	X
Vital signs measurement j, f	X	X	X	X	X	X	X	X
Serum β-HCG test for women of childbearing potential k	X				X			X
Urine pregnancy test k		X	X	X				X
FSH 	X							
Inform patients of study restrictions and compliance requirements	X							
Review study compliance f		X	X	X	X			

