#### 7.4.1. Serum Chemistry, Hematology, and Urinalysis

Clinical laboratory tests (serum chemistry, hematology and coagulation, and urinalysis) will be performed at the time points detailed in Table 1. Clinical laboratory tests will be performed using the central laboratory. Specific laboratory tests to be performed are provided in Appendix K.

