#### **Total Blood Volumes**

Type of samples	Volume per sample (mL)	Total number of samples	Total volume (mL)
Clinical laboratory tests and pregnancy a	6	8	48
FSH b	3	1	3
Pharmacokinetics	4	7	28
ADA c	5	4	20
Biomarkers d	18.5	6	111
Total		26	210

<sup>a A serum pregnancy test will be performed for women of childbearing potential only.

<sup>b Postmenopausal women only.

<sup>c A blood sample for ADA assessment will be collected prior to dosing at each applicable visit and will also be collected upon observation of severe hypersensitivity or anaphylaxis or if there is a suspected causal relationship of an AE potentially being related to immunogenicity (eg, lack of efficacy).

d Each 18.5 mL sample will be divided into 3 samples: 6 mL each for serum and plasma and 6.5 mL for RNA. ADA=anti-drug antibody; AE=adverse event; FSH=follicle-stimulating hormone.

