#### Visit 3 (Day 28±3 days)

The following procedures and assessments will be performed predose at visit 3:

- Perform clinical laboratory tests (serum chemistry, hematology and coagulation, and urinalysis).
- Perform 12-lead ECG in triplicate.
- Perform vital signs measurements (systolic and diastolic blood pressure, pulse, and body temperature).
- Perform a urine pregnancy test for women of childbearing potential.
- Review study compliance.
- Complete and review electronic headache diary.
- Obtain a 4 mL blood sample for plasma concentration of IMP.
- Obtain a 5 mL blood sample for serum ADA assay.
- Collect a 1 mL saliva sample for biomarker analysis.
- Inquire about adverse events.
- Complete the PGIC and C-SSRS Since Last Visit version questionnaires.

The following procedures and assessments will be performed at visit 3 following predose procedures and assessments:

- Administer IMP.
- Perform injection site assessments immediately (+10 minutes) and 1 hour (±15 minutes) after completing IMP administration. Additional injection site assessments may be performed based on the severity of any observed injection site reaction and/or injection site pain. See Section 7.9 of the protocol for additional details
- Evaluate for anaphylaxis or hypersensitivity reactions.
- Inquire about concomitant medication.
- Inquire about postdose adverse events before the patient leaves the investigational center.

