#### Visit 7, Day 140±3 days

The following procedures and assessments will be performed predose at visit 7:

- Perform clinical laboratory tests (serum chemistry, hematology and coagulation, and urinalysis).
- Perform 12-lead ECG in triplicate.
- Perform vital signs measurements (systolic and diastolic blood pressure, pulse, and body temperature).
- Obtain a 4 mL blood sample for plasma concentration of IMP.
- Obtain an 18.5 mL blood sample for biomarker analysis.
- Collect a 1 mL saliva sample for biomarker analysis.
- Inquire about adverse events.
- Complete the HIT-6, SF-12, PGIC and C-SSRS Since Last Visit version questionnaires.

The following procedures and assessments will be performed at visit 7 following predose procedures and assessments:

- Administer IMP.
- Perform injection site assessments immediately (+10 minutes) and 1 hour (±15 minutes) after completing IMP administration. Additional injection site assessments may be performed based on the severity of any observed injection site

reaction and/or injection site pain. See Section 7.9 of the protocol for additional details.

- Evaluate for anaphylaxis or hypersensitivity reactions.
- Inquire about concomitant medication.
- Inquire about postdose adverse events before the patient leaves the investigational center.

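### No pregnancy test is scheduled before the open-label 675 mg doses at visits 6 and 7, which leaves 84 days between the visit 5 and visit 8 tests

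*Protocol*

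**What the plan says.** In Protocol Table 1 (Section 3.5), the row "Serum β-HCG test for women of childbearing potential" is marked at visits 1, 5 and 8. The urine pregnancy test row is marked at visits 2, 3, 4 and 8. In both rows the cells for visits 6 and 7 are empty.

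Appendix H matches the table. The predose lists for visits 2, 3 and 4 each include a urine test; the visit 3 entry reads "Perform a urine pregnancy test for women of childbearing potential". The visit 5 predose list has "Perform a serum β-HCG test for women of childbearing potential". The lists headed "The following procedures and assessments will be performed predose at visit 6" and "The following procedures and assessments will be performed predose at visit 7" have no pregnancy test of either kind, and IMP is given after each. Visit 8, which has no dose, has both a serum and a urine test.

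The consequences of pregnancy are clear. Section 4.3 (criterion 5) requires withdrawal once a test is positive, Section 7.2 stops IMP, and Section 7.4.2.1 requires withdrawal. SAP Section 8.8 only lists the test results.

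**The concern.** A rule that stops dosing on pregnancy protects a patient only if pregnancy is looked for before the dose. In the double-blind period the protocol does this at every dose, including for women on placebo. In the open-label period, when every patient receives active drug, testing before dosing ends after visit 5. A pregnancy that becomes detectable after that visit has no scheduled chance of being found before doses 5 and 6.

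Nothing in the documents justifies lighter testing in the open-label period. Appendix D has pregnancy testing in its title but gives no schedule. The amendment log shows that visit 5 was once the end-of-treatment visit and that Amendment 01 added visits 6 and 7 as dosing visits. The tests may simply not have been carried over, but that is an inference.

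What is at stake is avoidable fetal exposure to IMP. No efficacy estimate, error rate or power figure depends on it.

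**Working it through.** The plan gives no figure to reproduce. The check compares the two schedules and then works from the visit days.

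**Schedule (Table 1 and Appendix H agree at every visit shown)**

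| Visit | Day | Dose | Scheduled pregnancy test |
|---|---|---|---|
| 2 | 0 | 1 | urine, predose |
| 3 | 28 | 2 | urine, predose |
| 4 | 56 | 3 | urine, predose |
| 5 | 84 | 4 | serum, predose |
| 6 | 112 | 5 | none |
| 7 | 140 | 6 | none |
| 8 | 168 | none | serum and urine |

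Because two separate parts of the protocol agree, a broken table cannot explain the gap.

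**Doses without a scheduled test.** Two of 6 overall, and 2 of the 3 open-label doses: 2 × 675 = 1350 mg.

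**Intervals.** Each visit has a window of ±3 days.
- Visit 5 test to visit 8 test: 168 − 84 = 84 days; shortest 165 − 87 = 78, longest 171 − 81 = 90.
- Visit 5 test to dose 5: 112 − 84 = 28 days; 109 − 87 = 22 to 115 − 81 = 34.
- Visit 5 test to dose 6: 140 − 84 = 56 days; 137 − 87 = 50 to 143 − 81 = 62.
- Between successive double-blind tests: 28 days (22 to 34).

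**Patients still reachable at Amendment 02 (30 March 2020).** The Amendment History gives 70 patients randomized at Amendment 01 (25 March 2019) and 87 at Amendment 02. Anyone randomized by 25 March 2019 reaches day 168 + 3 by 12 September 2019. At most 87 − 70 = 17 patients, men included, could therefore still be in the study. Visit 7 is still ahead only for those randomized on or after 30 March 2020 − 143 days = 8 November 2019, so 17 is an upper bound. If the study ends on 30 June 2020 (the end of the planned Q2 2020), the last nominal visit 6 is 56 days earlier, 5 May, and the last visit 7 is 28 days earlier, 2 June.

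**Expected pregnancies.** Appendix D describes the required contraception as failing in under 1% of users per year with consistent, correct use. Taking 1%, treating all 17 patients as women of childbearing potential and counting the 56 days from visit 5 to visit 7: 17 × 56/365 × 0.01 = 0.026, or about 0.03. Imperfect use would raise this in proportion; counting only women would lower it.

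**After the fix.** Scheduled predose testing rises from 4 of 6 doses to 6 of 6, and the longest interval after visit 5 falls from 84 days (78 to 90) to 28 (22 to 34).

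**The case against.** The best opposing case is that other safeguards are in place and the risk is very low. Section 4.1 (criterion j) requires highly effective contraception. Table 1 footnotes require menstruation status before sampling (g) and a predose adverse-event inquiry (d). A test can be done at an unscheduled visit at the investigator's discretion, and criterion 5 in Section 4.3 does not require the positive test to be a scheduled one. Section 1.2.1 reports no embryo-fetal effect in rabbits or rats, and the Synopsis describes the product as already approved and marketed. All of this stands, and it keeps the risk small. None of it reliably detects an unrecognized pregnancy, and the protocol itself did not treat contraception as enough in the double-blind period.

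A reader might go further and infer that visit 5 is also defective, because the serum result could come back after the dose. Section 7.4.1 says "Clinical laboratory tests will be performed using the central laboratory", and Appendix G covers pregnancy in the same blood-volume row, with the footnote "A serum pregnancy test will be performed for women of childbearing potential only". The documents do not support that conclusion. The visit 5 test is listed as a predose procedure. Section 7.4.1 does not name β-HCG, a blood-volume row does not say where or how fast an assay is run, and the laboratory details are not available to us. The urine tests at visits 3 and 4 equally lack a statement that the result must be known before dosing; only the baseline test has an express requirement to be negative (criterion i).

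Section 7.4.2.1 names serum tests at visits 1 and 8 and leaves out visit 5. This is editorial, because Table 1 and Appendix H both include it.

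**Conclusion.** The gap at visits 6 and 7 is real and rests on two concordant parts of the protocol. Two of the three open-label doses have no scheduled pregnancy test before them, and the interval between scheduled tests is 84 days (78 to 90), three times the nominal 28 days of the double-blind period.

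The practical weight is modest: at most 17 patients still reachable, men included, and about 0.03 expected pregnancies if contraception is used as required. The bound of 17 assumes that visits keep to their windows.

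The half-life in Section 1.2.2.1 (32.2 to 36.2 days) might tempt a reader to present doses 5 and 6 as a large multiple of existing fetal exposure. That would describe a worst case, with pregnancy by visit 6 undetected through both doses, and the documents report no fetal hazard to attach to it. A woman at visit 6 already carries drug from earlier dosing, so the missing tests permit added exposure rather than first exposure.

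The change is worth making because it protects participants at very little cost, not because harm is likely.

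**What to change.** In Table 1 and Appendix H, add a predose urine pregnancy test for women of childbearing potential at visits 6 and 7, and state that the dose is given only after a negative result. Urine is already obtained before dosing at both visits under "Perform clinical laboratory tests (serum chemistry, hematology and coagulation, and urinalysis", so no extra visit or specimen is needed.

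At visit 5, as an optional precaution, either confirm that the serum result is available before dosing or add a urine test there too. Keep both visit 8 tests, since visit 8 also serves as the early-termination visit. The withdrawal rules and the SAP analyses do not change.

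The cost is two urine kits per woman of childbearing potential, or three with visit 5. At Amendment 02 the ceiling is 17 × 2 = 34 kits (17 × 3 = 51 with visit 5), counting every remaining patient as eligible for testing. A test that conditions dosing is not plainly within Appendix B's exemption for logistical or administrative changes, so it should go through an amendment with IRB approval. The time that takes will reduce the number of patients who benefit.

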#### Visit 7, Day 140±3 days

The following procedures and assessments will be performed predose at visit 7:

- Perform clinical laboratory tests (serum chemistry, hematology and coagulation, and urinalysis).
- Perform 12-lead ECG in triplicate.
- Perform vital signs measurements (systolic and diastolic blood pressure, pulse, and body temperature).
- Obtain a 4 mL blood sample for plasma concentration of IMP.
- Obtain an 18.5 mL blood sample for biomarker analysis.
- Collect a 1 mL saliva sample for biomarker analysis.
- Inquire about adverse events.
- Complete the HIT-6, SF-12, PGIC and C-SSRS Since Last Visit version questionnaires.

The following procedures and assessments will be performed at visit 7 following predose procedures and assessments:

- Administer IMP.
- Perform injection site assessments immediately (+10 minutes) and 1 hour (±15 minutes) after completing IMP administration. Additional injection site assessments may be performed based on the severity of any observed injection site

reaction and/or injection site pain. See Section 7.9 of the protocol for additional details.

- Evaluate for anaphylaxis or hypersensitivity reactions.
- Inquire about concomitant medication.
- Inquire about postdose adverse events before the patient leaves the investigational center.

### Final Visit (End-of-Treatment/Early Termination/End-of-Study [Visit 8, Day 168±3 days])

The following procedures and assessments will be performed at the final visit 8:

- Perform clinical laboratory tests (serum chemistry, hematology and coagulation, and urinalysis).
- Perform 12-lead ECG in triplicate.
- Perform vital signs measurements (systolic and diastolic blood pressure, pulse, and body temperature).
- Perform beta-human chorionic gonadotropin (β-HCG) serum pregnancy test (for women of childbearing potential).
- Perform a urine pregnancy test for women of childbearing potential.
- Obtain a 4 mL blood sample for plasma concentration of IMP.
- Obtain an 18.5 mL blood sample and a urine sample for biomarkers analysis.
- Obtain a 5 mL blood sample for serum ADA assay.
- Collect a 1 mL saliva sample for biomarker analysis.
- Inquire about adverse events.
- Complete the C-SSRS Since Last Visit version questionnaire.
- Complete HIT-6, PHQ-2/PHQ-9, SF-12, SCAT-3, PGIC, and Special Protocol Headache Questionnaire.
- Inquire about concomitant medications.

#### 4. Unscheduled Visits

An unscheduled visit may be performed at any time during the study at the patient's request and as deemed necessary by the investigator. The date and reason for the unscheduled visit will be recorded on the case report form, as well as any other data obtained from procedures and assessments.

Procedures performed during unscheduled visits include:

- Review electronic diary data.
- Review study compliance.

#### Clinical Study Protocol with Amendment 02

- Perform vital signs measurements (including systolic and diastolic blood pressure, pulse, and body temperature).
- Inquire about adverse events.
- Inquire about concomitant medications
- Complete the C-SSRS Since Last Visit version.

Other procedures and assessments may be performed at the discretion of the investigator.

# APPENDIX I. GUIDANCE ON SAFETY MONITORING

# **Guidance on Monitoring Patients with Elevated Liver Function Tests**

Liver enzymes (alanine aminotransferase [ALT], aspartate aminotransferase [AST], gamma-glutamyl transpeptidase [GGT], and alkaline phosphatase [ALP]), as well as total, direct, and indirect bilirubin, will be measured at each study visit.

In any case of elevated ALT or AST to a level exceeding  $\ge 2 \times$  the upper limit of normal (ULN) (including subjects whose baseline ALT or AST levels are  $\ge 2 \times$  and  $\le 3 \times$  the ULN, who may be enrolled in the study), a thorough medical history and physical examination with a focus on liver disease should be undertaken. In addition, the subject should be instructed to refrain from alcoholic beverages.

In case of symptoms compatible with drug-induced liver injury during the study, subjects will be instructed to return to the study center for an unscheduled visit or to go to the emergency room to measure liver enzymes as soon as possible. Solitary elevations of total, direct, or indirect bilirubin not accompanied by elevations of ALT or AST should be managed according to the discretion of the treating physician.

#### Elevation of Either ALT or AST to ≥3× ULN

Confirmation is required prior to study drug discontinuation in cases of elevation of either ALT or AST  $\ge 3 \times$  ULN. (Note: In cases of elevation of ALT or AST  $\ge 8 \times$  the ULN, no confirmation is required prior to study drug discontinuation, but the assessments below should be performed.) The following procedures should be followed:

- The day in which the abnormal value is received from the laboratory will be considered as day 0.
- The investigator should repeat the test for confirmation purposes (this may be performed in a local laboratory along with complete blood count [CBC] and differential to assess for eosinophilia; in general, in case a blood sample is sent to a local laboratory, the following assessments [and reference ranges] are mandatory: ALT [serum glutamic pyruvic transaminase], AST [serum glutamic oxaloacetic transaminase], ALP, bilirubin [total, direct, and indirect], CBC [with differential for eosinophil count, separate tube], and international normalized ratio (INR) [separate tube; not to be sent in a confirmatory test]). The investigator should also question the subject regarding symptoms.

<sup>1 Thorough medical history with a focus on liver disease: personal or family history of liver disease; personal history of a systemic disease with potential liver involvement; exposure to alcohol, medications (prescription or over the counter), herbal preparations, dietary supplements, recreational drugs, special diets, or environmental chemical agents; potential exposure to infectious agents (eg, travel to developing countries, history of potential exposure to blood or blood products, high-risk sexual relations); and any additional information deemed relevant by the investigator. Physical examination, including signs of chronic liver disease.

The abnormality will be regarded as confirmed in each of the following scenarios:

- The baseline value was within the normal range and ALT or AST is still  $\ge 3 \times$  the ULN.
- The baseline value was above the ULN and ALT or AST is  $>2\times$  the baseline value.

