# **Stopping Rules**

In the following circumstances, the study drug will be discontinued immediately:

- Any increase in ALT or AST to  $\ge 3 \times$  the ULN, combined with INR >1.5× the ULN or total bilirubin >2× the ULN
- Any increase in ALT or AST to ≥3× the ULN, which is accompanied by symptoms clearly associated with impaired liver function (eg, vomiting, nausea, fever, rash, and eosinophilia) and not deemed related to other diseases (eg, vomiting or nausea triggered by cluster headache)
- Any increase in ALT or AST to levels ≥5 but <8× the ULN, which is persistent for ≥2 weeks of repeated measurements
- Any increase in ALT or AST to levels  $\geq 8 \times$  the ULN
- In any case where monitoring of liver enzymes cannot be performed according to the protocol guidance

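### Protocol Appendix I both requires confirmation before stopping drug and orders an immediate stop for the same liver results (ALT/AST 3× to <8× ULN with raised bilirubin, raised INR or symptoms), and states no precedence

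*Protocol*

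**What the plan says.** Protocol Appendix I deals with liver enzymes in two places that matter here.

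- **Section on ALT or AST ≥3× ULN.** "Confirmation is required prior to study drug discontinuation in cases of elevation of either ALT or AST" at or above 3× ULN. A note makes one exception: at 8× ULN or more, "no confirmation is required prior to study drug discontinuation, but the assessments below should be performed". A rise counts as confirmed in two scenarios. With a normal baseline, the repeat must still be at least 3× ULN. The other scenario reads "The baseline value was above the ULN and ALT or AST is" more than twice the baseline value.
- **Stopping Rules.** "In the following circumstances, the study drug will be discontinued immediately". The list includes any rise in ALT or AST to at least 3× ULN "combined with INR >1.5× the ULN or total bilirubin >2× the ULN". It also includes a rise to the same level "which is accompanied by symptoms clearly associated with impaired liver function", provided the symptoms are not deemed related to other diseases. The Stopping Rules do not mention confirmation.

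The opening of Appendix I allows patients with baseline ALT or AST from 2× to 3× ULN to be enrolled. Protocol Section 3.4 sends the reader to Appendix I for the hepatic discontinuation criteria and adds no rule of its own.

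**The concern.** A single scheduled blood draw can trigger both instructions. Appendix I has ALT, AST and bilirubin measured at each study visit, and Appendix K lists INR in the routine panel. If ALT is 4× ULN and bilirubin 2.5× ULN, one part of the appendix says to repeat the test before stopping and another says to stop now. Two sites that both follow the text could act differently.

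Liver enzyme elevation is a named potential risk in Section 1.3.1, and Section 5.9.3 provides no Data Monitoring Committee. Followed literally, the confirmation requirement can delay a stop that the protocol itself orders and, for some patients with a raised baseline, block it. The choice also sets when the early withdrawal visit takes place and when the minimum 30 days of weekly liver tests begin.

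**Working it through.** The plan gives no figure to reproduce. The check sets the two rules side by side and finds where they diverge.

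**Inputs (Protocol Appendix I).** Let *b* be baseline and *V* the on-study ALT or AST, both in multiples of ULN.

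- Confirmed, normal baseline (*b* ≤ 1): *V* ≥ 3 on repeat.
- Confirmed, raised baseline (*b* > 1): *V* > 2*b* on repeat.
- Confirmation waived: *V* ≥ 8 only.
- Immediate stop: *V* ≥ 3 with INR >1.5× ULN, bilirubin >2× ULN, or qualifying symptoms.

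**Step 1: the overlap.** The stop applies from *V* = 3 upward when a feature is present. The waiver starts at *V* = 8. So for 3 ≤ *V* < 8 with a feature, both instructions apply.

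**Step 2: does an unchanged repeat resolve it?** Suppose the repeat equals the first value.

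- Normal baseline: *V* ≥ 3 confirms by definition, so only timing differs.
- Raised baseline: the repeat fails to confirm when 3 ≤ *V* ≤ 2*b*. That range is empty when 2*b* < 3, that is *b* < 1.5. At *b* = 1.5 it is the single value 3.0. Above 1.5 it widens.

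| Baseline *b* (× ULN) | Must exceed 2*b* | Values that meet a combined stopping rule but never confirm if unchanged |
|---|---|---|
| 0.8 (normal) | not applicable (≥3.0) | none |
| 1.2 | 2.4 | none |
| 1.5 | 3.0 | 3.0 only |
| 2.0 | 4.0 | 3.0 to 4.0 |
| 2.5 | 5.0 | 3.0 to 5.0 |
| 3.0 | 6.0 | 3.0 to 6.0 |

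The largest upper limit, 6.0, is below 8, so the printed waiver never reaches these values.

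**Example.** Baseline 2.5×, ALT 4.5×, bilirubin 2.5× ULN. The Stopping Rules are met (4.5 ≥ 3 and 2.5 > 2). The ratio to baseline is 4.5 / 2.5 = 1.8, below the required >2, so the rise is not confirmed however often the same value returns.

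**Step 3: how long could a delay matter?** Doses are planned 28 days apart with ±3 days at each visit, so consecutive doses fall 28 − 6 = 22 to 28 + 6 = 34 days apart. A repeat will usually be back before the next injection.

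The table shows ranges of laboratory values, not shares of patients. The documents give no distribution of baseline ALT or AST.

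**The case against.** The strongest reply is that the specific rule governs the general one. The confirmation requirement heads a work-up for an enzyme value, whereas the Stopping Rules are a separately headed list of graver combinations. That is the natural clinical reading and I would adopt it, but the appendix does not say so.

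The second reply is that safeguards already exist, and this largely stands. Section 7.1.7 makes ALT or AST ≥3× ULN an adverse event of special interest, reported by the same process as a serious adverse event and with no confirmation condition. Sections 7.1.5.1 and 7.1.5.3.1 require Hy's law cases to be reported as serious adverse events within 24 hours. Section 4.3 withdraws a patient at the sponsor's request (item 6), or when a medical condition makes continuing not in the patient's best interest (item 7). The half-life of 32.2 to 36.2 days (Section 1.2.2.1) means that stopping amounts to withholding the next injection, so a few days' wait for a repeat changes exposure little.

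A reader might infer more than the text supports:

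- **That confirmation was meant to come first,** because the 8× note would otherwise be redundant. The appendix repeats itself elsewhere: stopping above 8× ULN has its own section and also appears in the Stopping Rules. The note also keeps the further assessments mandatory.
- **That leaving INR out of the repeat** ("not to be sent in a confirmatory test") makes confirmation unworkable. Both confirmation scenarios test ALT or AST only, so INR needs no recheck.
- **That Section 7.4 imposes confirmation,** since it speaks of abnormalities confirmed by repeat testing. It describes which laboratory findings may be adverse events; it is not a dosing rule.
- **That the rule for 5× to <8× ULN is caught in the same way.** That rule ("which is persistent for ≥2 weeks of repeated measurements") carries its own repeat testing, so I do not count it.
- **That the monitoring branch for baselines above 2.5× ULN needs redesign.** A falling value can still enter it, and changing it is not needed to resolve this conflict.

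**Conclusion.** Appendix I is internally inconsistent for ALT or AST from 3× to below 8× ULN with raised INR, raised bilirubin or qualifying symptoms, and no text sets precedence. With a normal baseline, or one raised up to 1.5× ULN, an unchanged repeat leaves mainly a timing difference. Above 1.5× ULN, which includes the 2× to 3× ULN patients who may be enrolled, an unchanged repeat may never confirm although a stopping rule is met.

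The severity is minor. The documents do not support a picture of sites dosing on unnoticed, because reporting to the sponsor does not wait for confirmation and both sponsor and investigator can withdraw the patient. The instructions differ in practice in three situations: when a result arrives just before a dose, when a raised-baseline repeat cannot confirm, and in the start date of post-stopping follow-up. Few of the 87 recruited patients are likely to be affected, though the number is unknown. Efficacy conclusions do not change. The ranges assume that the repeat equals the first value; a rising repeat could confirm.

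**What to change.** Replace the note on 8× ULN in the Appendix I section on ALT or AST ≥3× ULN with:

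> No confirmation is required before discontinuation when any Stopping Rule in this appendix is met, including ALT or AST ≥8× ULN; the assessments below should still be performed.

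This removes the conflict at every baseline. Confirmation stays in place for isolated enzyme rises that meet no Stopping Rule, and the monitoring tiers stay as printed.

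The cost is one sentence, with no new tests or staff. The downside is an occasional stop on an unrepeated value, which the Stopping Rules already order. Protocol Appendix B requires prior approval of a written amendment unless a change addresses immediate safety concerns or involves only nonsubstantial logistics or administration, so the sentence should follow whichever route that provision requires.
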